Pharmacologic Attenuation of Ketamine Using Nitroprusside
PI: [name]
NCT03102736
Document Date: April 15, 2019

 Mount Sinai	Protocol Title:	Pharmacologic attenuation of ketamine using nitroprusside
	Principal Investigator Name/Contact Info:	[name]/ [contact]
	Primary Contact Name/Contact Info	[name] / [contact]
	Date Revised:	4/15/2019
	Study Number:	HSM#16-00928/GCO#16-1580

MSSM Protocol Template HRP-503a

Brief Summary of Research (250-400 words):

Ketamine is an effective fast-acting therapeutic intervention for patients with treatment refractory depression that is known to have the unwanted effect of inducing temporary psychotomimetic symptoms (i.e., delusions, hallucinations and thought disorganization) in some patients. The precise mechanisms of these psychotropic effects remain to be elucidated, but for several decades the NMDA-type glutamate receptor has been hypothesized to be of central importance. In this vain, recent studies of the antihypertensive agent nitroprusside – which increases the availability of the molecular nitric oxide, a known by-product of NMDA activity – have found evidence for antipsychotic properties both in humans with psychotic illness and healthy subjects given ketamine. Here, we propose a study that will build on this work by evaluate the effects of nitroprusside on both the antidepressant and psychotomimetic effects of ketamine given to patients to treat refractory depression. In addition, as an exploratory aim, by collecting serial blood samples from participants as they are administered ketamine and nitroprusside, we will seek to determine functional markers of therapeutic effect and the mechanisms by which ketamine modulates both mood and psychotic states.

1) Objectives:

Research Question

We will test whether the effects of ketamine (KET) on mood and psychotic states is modified by co-administration with sodium nitroprusside (NP) in patients with depression. Furthermore, we will evaluate the extent to which the underlying biology of disease states and drug mechanisms can be inferred through analysis of peripheral blood biomarkers.

Specific Aims

Aim I. To test whether co-administration with NP has any impact on the efficacy of KET as an antidepressant.

Aim II: To test the ability of NP to prevent the psychotomimetic effects of KET in patients with depression.

 Mount Sinai	Protocol Title:	Pharmacologic attenuation of ketamine using nitroprusside

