Study drugs are administered on Study Visits 1 (single-blind) and 3 (double-blind). Visits 1 and 3 will occur up to four weeks apart to allow subject depression levels to return to baseline, a necessary component of the study design in order to test whether NP has any effect on the antidepressant action of KET. At Visit 1, participants will receive single-blind placebo (PLC) followed by KET (0.5 mg/kg/hour for 40 minutes), in which they are blind to the PLC/NP condition but are aware they are receiving KET. Subjects return to the clinic 24 hours following Visit 1, at which time their eligibility to continue and be randomized in the study is determined. The criteria for continuing is a significant antidepressant response to KET as demonstrated by MADRS score of $\geq 50\%$ improvement from baseline. Eligible subjects are randomized to one of two treatment conditions for Visit 3 (double-blind): PLC/KET or NP/KET (NP dose: 0.5 micrograms/kg/minute for 240 minutes), where again, the blinded condition is PLC/NP, but the subjects are aware they are receiving KET. Ineligible subjects (i.e., ketamine non-responders) will be scheduled to return to the clinic for an exit visit 1 week (7 ± 2 days) following the first infusion. The appearance of the nitroprusside will be protected to allow this drug to be blinded. Given the potential lengthy duration between visits (between 2 and 4 weeks), subjects will return to the clinic approximately 1 week (7 ± 2 days) following V1 (PLC/KET) for a check-in (Visit 2a) with the study doctor in order to ensure subject safety, as well as to be evaluated for remission of depressive symptoms. Additionally, a phone call MADRS will be administered 3 to 4 days following the in-person check-in, which will serve as the final determinant of the subject's return to baseline (defined as receiving a score within 20% of the baseline MADRS). If the subject has not returned to baseline, the V3 will be rescheduled for a date approximately two weeks following its initial appointment in order to allow maximum time (4 weeks) for a return to baseline, and the two check-ins (Visit 2a and by-phone check-in) will be repeated for the next two weeks, for a total of 4 additional check-ins. Following the V3 infusion visit, subjects again return to the clinic at 24 hours (Visit 4) and at 7 ± 2 days (Visit 5) following the second infusion day, and once more 14 ± 2 days after the infusion for the Exit Visit (Visit 6).

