Each treatment day (Visit 1 and 3) involves Infusion 1 (PLC or NP) and Infusion 2 (KET). Prior to Infusion 1 (PLC on Study Visit 1; PLC or NP on Study Visit 3) an indwelling catheter will be placed in the antecubital veins of each arm, and pulse, blood pressure, pulse-oximetry, and an EKG strip will be placed for continuous vital monitoring, which will be performed throughout the infusions. One of these catheters will be used for the administration of NP/PLC, and one will be used for the administration of KET; this is to ensure no interaction effects between the drugs given in the same line. At Time 0, Infusion 1 will begin through an infusion pump and will continue until Time 240 minutes. At Time 200

Protocol Title:	Pharmacologic attenuation of ketamine using nitroprusside
Principal Investigator Name/Contact Info:	[name]/ [contact]
Primary Contact Name/Contact Info	[name] / [contact]
Date Revised:	4/15/2019
Study Number:	HSM#16-00928/GCO#16-1580

minutes, Infusion 2 (KET on both Study Visits 1 and 3) will begin and will continue until Time 240 minutes, at which point all medication administration will be complete for the Study Visit. Clinical ratings (BPRS, CADSS, VAS; see below) will be collected at regular intervals before, during and after the infusion period by clinical raters. Blood draws may be conducted at baseline and Time +240 min on V1 and V3 infusion days, as well as at the 24-hour V2 and V4 visits, for a total of six blood draws; however, this is an optional procedure that will occur under a different protocol (GCO 11-1617). On the two infusion days, the blood will be drawn through one of the indwelling catheters that are used for study drug administration.

A urine toxicology screen will be performed before the first infusion and must be negative for illicit substances in order to proceed with the infusion. For females, a urine pregnancy test will confirm non-pregnancy prior to the infusions.

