- *Blood draws before/after infusion (if applicable)*
- *Clinical ratings before/during/following infusion*

Study Visit 1 will occur up to 4 weeks after Study Visit 0. At this Visit, all participants will first receive PLC for Infusion 1 and KET for Infusion 2. Details of the dosing and timing for these infusion sequences, as well as the associated clinical ratings and blood draws, is explained in the “Description of Study Drug Procedures” section above.

Study Visits 2 and 4 (24-h follow ups)

Participants will return to the study site 24 hours after Study Visit 1 for Study Visit 2. At this visit, safety and efficacy assessments will be performed (no drugs will be administered). The research team will analyze the outcomes of the MADRS and CADDs for each participant obtained on this day. In order to best assess the capacity of NP to attenuate the pro-psychotic and antidepressant effects of KET, only those participants who show improvement in MADRS $\geq 50\%$ compared to baseline will be eligible to return for Study Visit 3.

 Mount Sinai	Protocol Title:	Pharmacologic attenuation of ketamine using nitroprusside
	Principal Investigator Name/Contact Info:	[name]/ [contact]
	Primary Contact Name/Contact Info	[name] / [contact]
	Date Revised:	4/15/2019
	Study Number:	HSM#16-00928/GCO#16-1580

Participants who meet these criteria will return for Study Visit 3 up to 4 weeks later (depending on the amount of time required for the patient's MADRS score to return to baseline). These participants will be randomized to receive a drug administration sequence of either PLC/KET or NP/KET at Study Visit 3.

All patients who return for Study Visit 3 will return to the study site within 24 hours for Study Visit 4. At this visit, safety and efficacy assessments will be performed (no drugs will be administered).

Study Visits 2a and 5 (7-day follow-ups) and Phone Call Check-In

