The **Brief Psychiatric Rating Scale (BPRS)** (Overall and Gorham 1962) is used to assess acute behavioral changes during the infusions. Four key BPRS items for the positive (+) symptoms of psychosis will be used: conceptual disorganization, hallucinatory behavior, suspiciousness, and unusual thought content. Three items representing the negative (-) symptoms of psychosis will also be used: blunted affect, emotional withdrawal, and motor retardation.

The **Clinician-Administered Dissociative States Scale (CADSS)** (Bremner et al. 1998) is used to measure dissociative effects during the infusions. The scale includes 19 questions and 8 observer ratings scored from 0 (not at all) to 4 (extremely). The CADSS measures impairment in body perception, environmental perception, time perception, memory impairment, and feelings of unreality.

Visual Analog Scales. These scales are scored in millimeters from the left-hand side of a 100-mm line to a perpendicular mark made by the patient at a point corresponding to the apparent magnitude of the feeling state. Range: 0 ("not at all") to 100 ("most ever").

Montgomery-Asberg Depression Rating Scale (MADRS) (Montgomery and Asberg 1979). This is a 10-item instrument used for the evaluation of depressive symptoms in adults and for the assessment of any changes to those symptoms. Each of the 10 items is rated on a scale of 0 to 6, with differing descriptors for each item. These individual item scores are added together to form a total score, which can range between 0 and 60 points. The estimated time to administer this scale is 20 minutes. Inter-rater reliability of the scale is high and scores correlate significantly with those of the HAM-D. On the infusion days a modified MADRS will be used that will exclude the sleep and appetite items.

Quick Inventory of Depressive Symptomatology, Self Report (QIDS-SR): The Quick Inventory of Depressive Symptomatology, Self Report (QIDS-SR) is a 16-item self rated instrument designed to assess the severity of depressive symptoms. The 16 items cover the nine symptom domains of major depression as indicated by the DSM, and are rated on a scale of 0-3. Total scores range from 0 to 27, with ranges of 0-5 (normal), 6-10 (mild), 11-15 (moderate), 16-20 (moderate to severe), and 21+ (severe).

Columbia-Suicide Severity Rating Scale (C-SSRS): The Columbia-Suicide Severity Rating Scale (C-SSRS) is a comprehensive, semi-

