The reported incidence of KET-induced perceptual disturbances varies from less than 5% to greater than 30% (Knox et al. 1970; White et al. 1980) and may manifest as vivid dreaming, visualization of psychedelic color, suspension in space, kaleidoscopic floating, and out-of-body experiences. Some patients describe these psychic experiences as bizarre or frightening, while others find them pleasurable, joyful, and fascinating. Indeed, KET is also known as “Special K” as a drug of abuse related to PCP. For that reason KET was placed in Schedule III of the Controlled Substance Act in 1999. Nonetheless, when perceptual disturbances occur, they are usually mild and of short duration (Green and Johnson 1990). KET administration has transient effects on symptoms, usually lasting less than 60 minutes and rarely lasting longer than 2 hours (Carpenter 1999). The perceptual disturbances may be more common in those with preexisting psychosis (Lahti et al. 1995).

Several studies have addressed the question of prolonged psychological effects in the general population secondary to its anesthetic use and concluded that KET does not place patients at a greater risk than other anesthetics (Hersack 1994; Reich and Silvay 1989; Schorn and Witwam 1980). There is no evidence in these long-term studies that individuals exposed to KET are at risk of abusing it on follow-up.

Both ourselves and others have safely used KET in a large number of psychophysiological studies in patients with psychiatric disorders as well as in healthy with doses similar to that of the present study. A meta-analysis of a number of these studies found no evidence of behavioral sensitization following repeated KET exposure (Cho et al. 2005).

7) Provisions for Research Related Injury

We have described above the potential risks of the research procedures and the safeguards that will be used to minimize risks. These include termination of research participation if it is believed that such participation endangers a patient's welfare. Monitoring procedures are used to evaluate potential side effects of treatment or of research procedures. The protocol stipulates an extensive medical and psychiatric evaluation of all patients as a condition for research participation.

 Mount Sinai	Protocol Title:	Pharmacologic attenuation of ketamine using nitroprusside
	Principal Investigator Name/Contact Info:	[name]/ [contact]
	Primary Contact Name/Contact Info	[name] / [contact]
	Date Revised:	4/15/2019

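### The run-in is said to select for both effects of ketamine but selects on MADRS alone, and the Visit 1 infusion ratings are not used as a baseline for the randomised psychotomimetic comparison

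*Combined protocol and SAP*

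**What the plan says.** **Purpose of the selection.** Section 5(f), Study Visits 2 and 4: "In order to best assess the capacity of NP to attenuate the pro-psychotic and antidepressant effects of KET, only those participants who show improvement" of at least 50% on the MADRS are eligible for Visit 3.

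**Criterion.** Description of Study Drug Procedures, also in 5(f), gives the same single rule: "The criteria for continuing is a significant antidepressant response to KET as demonstrated by MADRS score of" at least 50% improvement from baseline. No BPRS, CADSS or VAS threshold appears.

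**CADSS at the eligibility visit.** For Visit 2, 24 hours after the infusion: "The research team will analyze the outcomes of the MADRS and CADDs for each participant obtained on this day". No decision is tied to the CADSS result. The instrument description says that the CADSS "is used to measure dissociative effects during the infusions".

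**Duration of the effect.** Section 6, Risks associated with KET: "KET administration has transient effects on symptoms, usually lasting less than 60 minutes and rarely lasting longer than 2 hours".

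**Ratings on infusion days (Visits 1 and 3).** "Clinical ratings (BPRS, CADSS, VAS; see below) will be collected at regular intervals before, during and after the infusion period by clinical raters".

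**Outcome and model.** Section 5(e) makes change in the BPRS positive items, CADSS and VAS primary outcome (b), compared across PLC/KET and NP/KET administrations. The model is a repeated measures General Linear Model with Time and Treatment Condition both within-subject. The Visit 1 reaction is not named as a covariate or stratifier.

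**The concern.** The stated purpose covers two effects and the criterion tests one. Nothing in the documents shows that a MADRS response at 24 hours predicts a psychotomimetic reaction during the infusion. The Background cites one rodent study as suggesting separate pathways for the two kinds of symptom and another that makes nitric oxide part of the antidepressant mechanism, and it leaves the question open.

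Aim II asks whether NP prevents psychotomimetic effects, and the Brief Summary says these occur in only some patients. A patient who stays at the floor on PLC/KET at Visit 1 leaves NP little to prevent at Visit 3. With a target of 40 randomised patients, differences in reactivity are also a large source of noise. Each patient's reactivity has been measured before randomisation, so leaving it out of the randomised comparison gives up precision that costs nothing to obtain.

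**Working it through.** **1. Stated purpose against rule.** Purpose: pro-psychotic and antidepressant effects. Rule: MADRS improvement of at least 50%. The pro-psychotic half of the purpose has no matching criterion.

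**2. Can the 24-hour CADSS stand in?** The effect usually ends within 60 minutes and rarely lasts beyond 2 hours. A rating at 24 hours is 12 times the longer of these limits (24 / 2). It can be expected to say little about the acute reaction, and it decides nothing.

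**3. Does the planned model already use Visit 1?** All patients receive PLC/KET at Visit 1.
- Patients randomised to PLC/KET have the same condition twice, so they give no within-subject treatment contrast.
- In patients randomised to NP/KET, Visit 1 v Visit 3 is a treatment contrast, but treatment is confounded with order.
- The randomised contrast is Visit 3 between arms, and the stated model does not adjust that contrast for Visit 1.

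**4. What adjustment would gain.** The plan gives 40 as a goal, with no alpha, power, effect size or SD, so there is no figure to reproduce. Assumptions: 20 per arm (the allocation ratio is not stated), equal variance at both visits, a linear relation, and correlation r between Visit 1 and Visit 3 change on the same scale. The documents give no r.

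Adjusted variance / unadjusted variance = 1 − r². Equivalent unadjusted arm size = 20 / (1 − r²). Smallest detectable standardised difference (two-sided 5%, 80% power, normal approximation): unadjusted (1.96 + 0.84) × √(2/20) = 0.89; adjusted 0.886 × √(1 − r²).

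| r (assumed) | 1 − r² | Equivalent n per arm | Detectable difference |
|---|---|---|---|
| 0 | 1.00 | 20 | 0.89 |
| 0.3 | 0.91 | 22 | 0.85 |
| 0.5 | 0.75 | 27 | 0.77 |
| 0.7 | 0.51 | 39 | 0.63 |

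**5. What adjustment would cost.** One degree of freedom, plus a small inflation from chance differences in the covariate. For a normal covariate the inflation is 1 + 1/(2n − 4) = 1 + 1/36 = 1.028 at n = 20. It breaks even at r² = 1 − 36/37 = 0.027, or r of about 0.16.

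**6. Dilution.** If NP acts only in patients who react, the mean effect in the arm is p times the effect in reactors, where p is the proportion reacting. The documents give no p for these scales at this dose, so no figure follows.

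**7. Chance imbalance, illustration only.** Suppose K of 40 patients are reactors, arms are fixed at 20:20 and nothing is adjusted. X, the number of reactors in one arm, is hypergeometric. The probability that the arms differ by 4 or more reactors, P(|2X − K| ≥ 4), is 0.30 for K = 12 and 0.24 for K = 8. Both values of K are assumed.

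**The case against.** **The within-subject model already makes each patient his or her own control.** This is partly right: the Visit 1 ratings do enter as PLC/KET administrations. But the contrast they supply is confounded with order in one arm and absent in the other. If the plan is read generously, as comparing Visit 3 minus Visit 1 between arms, the variance relative to Visit 3 alone is 2(1 − r): 1.4 at r = 0.3, 1.0 at 0.5, 0.6 at 0.7. Covariate adjustment (0.91, 0.75, 0.51) does better at each value.

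**Chance imbalance is not bias.** This stands. A valid test allows for it, so the probabilities in step 7 describe lost precision in an unadjusted analysis and not a false-positive problem.

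**A MADRS-only criterion suits Aim II.** This also stands. The Background's goal is to reduce unwanted effects in patients treated for depression, so antidepressant responders are a sensible population. What needs changing is the rationale and the analysis.

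**The 24-hour CADSS does no harm.** True, since nothing depends on it. The visit schedule (Table 1) is not in the text available to me and may give more detail on ratings.

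**Two stronger readings are tempting.** A reader might infer that Aim II is tested in patients with no documented effect to attenuate. The infusion-day ratings contradict that: the reaction is recorded at Visit 1 but not required. A reader might also take the statement in Section 6 that "The reported incidence of KET-induced perceptual disturbances varies from less than 5% to greater than 30" percent and conclude that only 2 to 12 of 40 patients react (40 × 0.05 and 40 × 0.30), with the effect diluted to match. The documents do not support this. The range is open at both ends, it is not tied to this dose, and the two references cited for it concern, by their titles, induction agents and surgical patients. It also counts reported perceptual disturbances, whereas outcome (b) is change in scores.

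**Conclusion.** The point holds in a limited form. The claim that the run-in best serves the assessment of the pro-psychotic effect is not backed by its only criterion, and the CADSS cited at that decision is normally too late to show the effect. Randomised patients may or may not have reacted at Visit 1. Their recorded reaction is not used as a baseline for the randomised Visit 3 comparison, so outcome (b) is less precise than it could be.

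The gain from adjustment is a residual variance of about 0.75 of the unadjusted value at r = 0.5, within a range of 0.91 to 0.51 for r from 0.3 to 0.7. This rests on an assumed correlation, assumed equal allocation and an approximately linear relation. Scores bunched at the floor would strain the last of these. Dilution by patients at the floor is real in direction and unknown in size.

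**What to change.** 1. Keep the MADRS criterion. In the Visits 2 and 4 section, drop the claim that it selects for the pro-psychotic effect, and refer to the Visit 1 infusion-day ratings in place of the 24-hour CADSS.
2. Analyse outcome (b) as a between-arm comparison of Visit 3 change during the ketamine infusion, with each patient's Visit 1 change on the same scale as a continuous covariate.
3. Pre-state a supporting analysis of treatment by Visit 1 reaction, to show whether any NP effect is confined to patients who reacted. With 40 patients it will be imprecise and should be labelled supportive.
4. Optionally, stratify Visit 3 randomisation on Visit 1 reaction, with a cut fixed in advance. The documents offer no basis for a cut and a stratum could be nearly empty, so the continuous covariate matters more.
5. Reconcile the rating window. Section 5(e) sets outcome (b) at Time 0 to 40 minutes, while Description of Study Drug Procedures starts Infusion 1 at Time 0 and ketamine at Time 200. Read literally, the window closes before ketamine begins. Step 2 needs one agreed window for both visits.

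Cost: a few sentences of protocol text, one degree of freedom per covariate and, if stratified, one factor to manage. No extra assessments or patients.
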